Appendix 1. Calculation of CHW Statistics

Calculation of the CHW Statistics for Primary Analysis

As pointed out by Mehta and Pocock (2010), regardless of the rule for increasing the sample size following interim analysis, if the conventional Wald statistic is replaced by the CHW statistic, then the Type I error is preserved (Cui et al. 1999). This section describes the approach to calculating the CHW statistic using the primary MMRM analysis results.

Table APP1.1. Defining the Quantities for the CHW Test Statistic

Quantity	Input Value or Derivation/Calculation
z_1	This is the associated test statistic for the LSMean difference of LY2951742 (300 mg) versus placebo for the primary efficacy analysis conducted using only patients included in the interim assessment . The LSMean contrast should be conducted such that a positive value for the test statistic should indicate a favorable treatment effect LY2951742 (300 mg) relative to placebo, that is LSMean for placebo – LSMean for LY2951742 (300 mg).
z_2	This is the associated test statistic for the LSMean difference of LY2951742 (300 mg) versus placebo for the primary efficacy analysis conducted using only the set of patients included in the post-interim assessment . The LSMean contrast should be conducted such that a positive value for the test statistic should indicate a favorable treatment effect LY2951742 (300 mg) relative to placebo, that is LSMean for placebo – LSMean for LY2951742 (300 mg).
n_1	This is the pre-specified total number of randomized patients included in the interim analysis for both the LY2951742 (300 mg) treatment group and the placebo treatment group. These are patients randomized on or before the randomization cutoff date who had the opportunity to complete the trial, regardless of whether they provided postbaseline data to the interim analysis. The interim is scheduled to occur when 70% of randomized patients have had the opportunity to complete the treatment phase at $n_1 = 114$.
n_2	This is the pre-specified planned increment from n_1 for the total number of patients in both the LY2951742 (300 mg) and placebo treatment groups should the study remain at the planned minimum sample size based on interim results. The planned minimum sample size is 162 and if the interim occurs at the planned $n_1 = 114$, the increment needed to get to 162 patients is $n_2 = 48$.

Given the quantities defined in the above Table APP1.1, the final CHW test statistic for the primary efficacy analysis (at the completion of the treatment phase after the sample size increase) can be written as a weighted combination of the independent increments comprising the interim Wald test statistic and the post-interim Wald test statistic (Cui et al. 1999; Mehta and Pocock 2010):

$$z_{chw} = \left(\frac{\sqrt{n_1}}{\sqrt{n_1 + n_2}} z_1 + \frac{\sqrt{n_2}}{\sqrt{n_1 + n_2}} z_2 \right).$$

The CHW test statistic will also be applied to the gated secondary outcomes if the sample size is increased based on the interim results of the primary efficacy analysis. Specifically, the values of z_1 and z_2 will be calculated based on the analysis for the secondary outcome in order to calculate the z_{chw} value, and the quantities of n_1 , and n_2 that define the weights for the CHW test statistic will remain as given in Table APP1.1. For gated secondary outcomes that are binary, it is well known that the Chi-squared test for comparing 2 proportions is equivalent to the Wald test for comparing 2 binomial proportions. The z_1 and z_2 will be derived by applying the inverse normal cumulative distribution function (Φ^{-1}) to the chi-square p-values with appropriate sign.

Then, the preceding formula for the z_{chw} test statistic will also be utilized for the binary gated secondary outcome.

Calculation of the CHW Statistics for Permutation Test of Primary Measures

As summarized in Section 5.5.11, sensitivity analysis for primary analysis using permutation test will also be conducted. If the sample size is not increased, the permutation test will be performed on the complete data and the CHW procedure will not be applied. If the sample size is increased, then the permutation test will be performed on patients before and after the interim analysis. These results will be combined using the CHW procedure. This section describes the approach.

Table APP1.2. Additional Definitions for CHW Test Statistic for the Permutation Test

Quantity	Input Value or Derivation/Calculation
p_1^p	This is the p-value derived from the permutation test of the primary efficacy analysis using only patients included in the interim assessment . The p-value is derived from the permuted distribution of test statistics as described in Section 5.5.11.
z_1^p	This is the z-statistic from the permutation test of the primary efficacy analysis using only patients included in the interim assessment . A positive value for the z-statistic should indicate a favorable treatment effect LY2951742 (300 mg) relative to placebo, that is LSMean for placebo – LSMean for LY2951742 (300 mg). This quantity is derived by applying the inverse normal cumulative distribution function (Φ^{-1}) to the permutation p-value, p_1^p . Therefore,
	$z_1^p = \text{sign} * \Phi^{-1}(1 - p_1^p/2)$
p_2^p	This is the p-value derived from the permutation test of the primary efficacy analysis using only the set of patients included in the post-interim assessment . The p-value is derived from the permuted distribution of test statistics as described in Section 5.5.11.
z_2^p	This is the z-statistic from the permutation test of the primary efficacy analysis using only the set of patients included in the post-interim assessment . A positive value for the test statistic should indicate a favorable treatment effect LY2951742 (300 mg) relative to placebo, that is LSMean for placebo – LSMean for LY2951742 (300 mg). This quantity is derived by applying the inverse normal function to the permutation p-value, p_2^p . Therefore,
	$z_2^p = \text{sign} * \Phi^{-1}(1 - p_2^p/2).$

Given the quantities defined in the above Table APP1.1 and Table APP1.2, the final CHW test statistic for the permutation test can be written as a weighted combination of the independent increments comprising the interim test statistic and the post-interim test statistic (Cui et al. 1999; Mehta and Pocock 2010):

$$z_{chw}^p = \left(\frac{\sqrt{n_1}}{\sqrt{n_1 + n_2}} z_1^p + \frac{\sqrt{n_2}}{\sqrt{n_1 + n_2}} z_2^p \right).$$

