SP III/IV/V Combined (GMB-treated time + post treatment time)		2) patients who received placebo during SP III and entered the open-label phase with at least one galcanezumab injection.	

Abbreviations: ePRO = electronic patient reported outcome; GMB = galcanezumab; SP = study phase.

a Analyses in SP III and first 4 weeks of SP IV combined, will be conducted for ePRO data only.

Treatment effects will be evaluated based on a 2-sided significance level of 0.05 for all the other efficacy and safety analyses. Ninety-five percent (95%) CI for the difference in least-square means (LSMeans) between treatment groups will be presented. Adjustments for multiple comparisons for the analyses corresponding to the primary and gated secondary objectives are described in the sections on the primary and secondary efficacy analyses below. There will be no adjustments for multiplicity for analyses of other data.

A repeated measures analysis refers to a restricted maximum likelihood (REML)-based, mixed-effects repeated measures (MMRM) analysis using all the longitudinal observations at each postbaseline visit/week.

Categorical comparisons between treatment groups for safety measures will be performed using Fisher's exact tests, where appropriate.

Any change to the data analysis methods described in the protocol will require an amendment ONLY if it changes a principal feature of the protocol. Any other change to the data analysis methods described in the protocol, and the justification for making the changes, will be described in the SAP and/or in the clinical study report.

Additional exploratory analyses of the data will be conducted as deemed appropriate.

Statistical analysis of this study will be the responsibility of Eli Lilly and Company (Lilly) or designee. SAS®software will be used to perform most or all statistical analyses.

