5.5.11. Sensitivity Analysis

Dynamic Allocation (Minimization) Assumption

A permutation test will be performed as a sensitivity analysis of the primary MMRM analysis to confirm the results of the asymptotic inference. The key features of the permutation test which will be employed are as follows:

- The patients' baseline covariates, responses, and enrollment order will be considered fixed.
- The sharp null hypothesis will be assumed (that is, responses to GMB and placebo will be assumed exactly equal).
- The exact minimization algorithm and exact site pooling algorithm will be used to generate the null distribution of the primary test statistic from the MMRM analysis.
- The p-value based on the generated null distribution (that is, permutation test p-value) will be obtained by comparing the observed test statistic value to the percentiles of the generated null distribution.

Explicitly, the p-value is derived from the permuted distribution of test statistics as follows. If the total number of permutations is m , and b of these permutations have a test statistic greater than or equal to the observed test statistic, z , then the permutation p-value, p^p is,

$$p^p = \frac{b + 1}{m + 1}$$

where m equals 100,000. As discussed in Phipson and Smith 2010, this is an upper bound on the estimated p-value. This method is used to generate the approximate null distribution. Note that the described permutation p-value calculation should be conducted such that a positive value for the test statistic should indicate a favorable treatment effect GMB 300 mg relative to placebo.

If the sample size is not increased based on the interim results, the permutation test will be performed on the combined data from the interim and post-interim assessments since the CHW procedure will not be applied. If the sample size is increased, then the permutation test will be

performed on patients before and after the interim analysis. These results will be combined using the CHW procedure. The details of computing CHW statistics for the permutation test is summarized in [Appendix 1](#).

Missing Data Assumption

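### The permutation p-value is one-sided in SAP Section 5.5.11 but is converted as two-sided in Table APP1.2, so after a sample-size increase the permutation check is biased toward galcanezumab

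*SAP*

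**What the plan says.** SAP Section 5.5.11, under the dynamic allocation assumption, states its purpose: "A permutation test will be performed as a sensitivity analysis of the primary MMRM analysis". The p-value is (b + 1)/(m + 1) with m = 100,000, where b of m "of these permutations have a test statistic greater than or equal to the observed test statistic". The direction is fixed as well: "a positive value for the test statistic should indicate a favorable treatment effect GMB 300 mg relative to placebo".

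Without a sample-size increase, the test is run once on all the data. Otherwise Appendix 1 applies: "If the sample size is increased, then the permutation test will be performed on patients before and after the interim analysis". The two stage results are then combined with the Cui, Hung and Wang (CHW) weights. Table APP1.2 takes its stage p-values by cross-reference: "The p-value is derived from the permuted distribution of test statistics as described in Section 5.5.11". It converts the first with "z_1^p = \text{sign} * \Phi^{-1}(1 - p_1^p/2") and the second in the same form. It does not define the sign factor beyond giving the orientation of the result: "A positive value for the z-statistic should indicate a favorable treatment effect LY2951742 (300 mg) relative to placebo".

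On levels, Section 5.5.1 says: "Treatment effects will be evaluated based on a 2-sided significance level of 0.05 for all the other efficacy and safety analyses". Sections 5.5.1.4 and 5.5.8.1 set one-sided 0.025 for the primary analysis. Both levels have the same upper-tail cut-off, 1.96.

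**The concern.** A count of permuted statistics at or above the observed value, with no absolute value and no doubling, is an upper-tail p-value. The matching z is Φ⁻¹(1 − p). Halving p before inverting, then attaching a sign, is the conversion for a two-sided p-value. Applied to a one-sided p-value, it halves a quantity that already refers to one tail.

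The permutation test is the SAP's check that the asymptotic MMRM inference holds under minimisation. If its z is inflated whenever a stage favours galcanezumab, it confirms a positive primary result too easily. It can also look significant beside a primary result that is not.

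**Working it through.** **Inputs.** From Table APP1.1: n1 = 114 and n2 = 48, total 162. The weights are w1 = √(114/162) = 0.8389 and w2 = √(48/162) = 0.5443. The benchmark is one-sided 0.025, z = 1.96.

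**Assumptions.** Under the null, the stage statistics T1 and T2 are independent standard normal. The permutation p-value is p = 1 − Φ(T). The sign factor is the sign of the observed statistic (placebo LSMean minus galcanezumab LSMean).

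**The plan's own level.** With z = Φ⁻¹(1 − p) = T at each stage, the combination w1·T1 + w2·T2 has variance 0.8389² + 0.5443² = 1. It exceeds 1.96 with probability 0.0250, as intended.

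**One stage as written.**
- T = 1.00 gives p = 0.159 and a formula z of 1.41.
- T = 1.645 gives p = 0.050 and z = 1.96.
- T = −1.00 gives p = 0.841 and z = −0.20.
- T = −3.00 gives z = −0.002.

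Favourable stages (p < 0.5) are always inflated. For unfavourable stages the right value is Φ⁻¹(1 − p) and the formula gives −Φ⁻¹(1 − p/2). The two are equal when 1 − p = p/2, that is at p = 2/3. Between 0.5 and 2/3 the formula is too negative; above 2/3 it is too close to zero, so a worse result earns a better z.

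**Worked example, stage p-values 0.05 and 0.20.**
- Correct: 0.8389 × 1.645 + 0.5443 × 0.842 = 1.84, one-sided p = 0.033.
- As written: 0.8389 × 1.960 + 0.5443 × 1.282 = 2.34, one-sided p = 0.010.

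The example misses 0.025 when done correctly and meets it as written.

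**Error if the formula were always applied.** By numerical integration, the probability that the combined z exceeds 1.96 under the null is 0.0799. This splits into 0.0248 where the correct combination is also significant and 0.0551 where it is not. Simulation agrees (0.080), and using the discrete p-value with m = 100,000 does not change it. The lowest possible combined z is −0.674 × (0.8389 + 0.5443) = −0.93, so the lower-tail rejection rate is 0 instead of 2.5%.

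**Error when used only after an increase.** The re-estimation rule is not in these documents, so these are assumed bands of interim z that trigger an increase. The formula is used inside the band and the correct combination outside it.

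| Interim z leading to an increase | Overall error |
|---|---|
| 1.6 to 1.96 | 3.4% |
| 1.2 to 1.96 | 5.1% |
| 1.0 to 1.96 | 5.8% |
| 0.5 to 1.96 | 7.0% |
| 0 to 1.96 | 7.4% |

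For the last four bands, a futility stop at interim z below 0 changes these figures by less than 0.01 percentage point.

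**Value as a check (illustration only).** Suppose minimisation left the stage Wald statistics with a null SD of 1.1, while the permutation p-values stayed exact. The primary null error would be P(Z > 1.96/1.1) = 3.7%. A correct permutation combination would be significant in 0.025/0.0374 = 67% of those falsely significant primaries, so it would flag about a third. The formula as written, if always applied, is significant in 98%. Confined to trials with an increase, for the bands 1.2 to 1.96 and 0.5 to 1.96, it is significant in 100% of the falsely significant primaries.

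**The case against.** **The test decides nothing.** The SAP attaches no rejection threshold to the combined permutation statistic, and success rests on the primary CHW test. This stands. A spuriously significant permutation result could not rescue a failed primary, and a reader comparing the two z values might notice the gap. It limits the consequence but does not make the formula right.

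**The 8.0% is a ceiling.** The SAP uses the formula only after an increase, and narrow bands give less. This also stands: 8.0% is not the plan's operating error rate. The bands tried still gave 3.4% or more, above 2.5%. The illustrative SD of 1.1 is likewise assumed; nothing in the documents says minimisation inflates the statistic to that degree. Counted over all trials rather than only those with an increase, the 98% falls to between 82% and 88% for the two bands named above.

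**A two-sided p-value was probably intended.** The sign factor and p/2 make sense only for one, Section 5.5.1 works at two-sided 0.05, and the Version 5 revision history says formulas in Table APP1.2 were corrected. That may well be the intention. But a significance level does not change which permutations Section 5.5.11 counts, no passage redefines the p-value, and the mismatch is in the current text. A programmer following both sections would code the one-sided count and then halve it.

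**Conclusion.** The two passages are incompatible, and the SAP is wrong as written. After a sample-size increase, the permutation test overstates evidence for galcanezumab: z = 2.34 instead of 1.84 in the worked example, and a null rejection rate of 8.0% instead of 2.5% if the formula were always used. Overall error of about 3.4% to 7.4% depends on the assumed increase bands. The figures rest on approximately normal permutation distributions and on reading the undefined sign factor as the sign of the observed statistic.

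The primary and gated CHW tests are not affected, nor is the permutation test when the sample size stays as planned. This should be fixed, because the error favours the sponsor's product in the analysis meant to confirm the primary inference.

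**What to change.** Make the two sections agree before unblinding, in one of two ways:

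1. Keep the one-sided p-value of Section 5.5.11 and change Table APP1.2 to z = Φ⁻¹(1 − p) for both stages, with no halving and no sign factor.
2. Keep the Table APP1.2 formula, redefine the Section 5.5.11 p-value as two-sided by counting permutations whose absolute statistic is at least the absolute observed value, and state that the sign is that of the observed placebo-minus-galcanezumab difference.

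Both gave 0.0250 when checked. The SAP should say which applies, because a choice made after results are known would look outcome-driven. The cost is a one-line edit and no new data. Under the first option the stage p-values do not change. After an increase, favourable stages will look less favourable than under the present formula.

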Appendix 2. Description of Important Protocol Deviations

Category	Subcategory	Study specific term	Source
Informed Consent Form (ICF)	Informed consent not obtained		Programmable
	Improper consent	ICF not signed prior to initiation of protocol procedures	Nonprogrammable
Eligibility	Inclusion/ Exclusion	At Visit 1 patients must have a history of chronic cluster headache	Nonprogrammable
		Age < 18 or > 65 years old at study entry	Nonprogrammable
		Female patients who have a positive serum pregnancy test prior to Visit 3	Programmable
		Randomized patients had prior or current exposure to CGRP antibody	Nonprogrammable
		Corrected QT (QTcB) interval > 470 msec for women and > 450 for men prior to Visit 3	Nonprogrammable
		PR > 220, or conduction delay of QRS > 120 prior to Visit 3	Nonprogrammable
		SBP > 160 mmHg or DBP > 100 mmHg on 2 or more blood pressure assessments prior to Visit 3	Programmable
		Evidence of ischemia /qualitative findings of ST or J-point elevation, excluding early repolarization	Nonprogrammable
		History of MI, UA, PCI, CABG or DVT/PE within 6 months of screening.	Nonprogrammable

Category	Subcategory	Study specific term	Source
Eligibility	Inclusion/ Exclusion	Have planned cardiovascular surgery or percutaneous coronary angioplasty	Nonprogrammable
		Any lifetime history of vasospastic angina or stroke	Nonprogrammable
		Clinical evidence of peripheral vascular disease or a diagnosis of Raynaud's Phenomenon	Nonprogrammable
		Have any history of intracranial or carotid aneurysm, intracranial hemorrhage, stroke.	Nonprogrammable
		Have a history of intracranial tumors or significant head trauma that preclude study participation	Nonprogrammable
		Have a clinically significant elevation of ≥ 2 X ULN for ALT, or ≥ 1.5 X ULN for TBIL or ALP prior to Visit 3	Nonprogrammable
		Have a positive urine drug screen for substances of abuse not allowed prior to randomization	Programmable
		Completion of less than 5 of 7 days per week of the daily ePRO diary during the baseline assessment	Programmable
		Baseline weekly cluster headache attack: (a) ≥ 2 consecutive days without attack, or (b) < 8 total attacks, or (c) > 8 attacks per day	Programmable
		Body mass index (BMI) ≥ 40 kg/m ² at baseline.	Programmable
		Use within 14 days prior to SP II or in SP II/III/IV of any of the medications described in I/E 9a	Programmable
		Use within 30 days prior to SP II or in SP II/III/IV of any of the medications described in I/E 9b	Programmable

Category	Subcategory	Study specific term	Source
Study Procedures	Other	Use of Botox within 4 month prior to SP II and during study	nonprogrammable
		Use of other excluded meds during study	Nonprogrammable
		Use of verapamil at doses higher than allowed at baseline and during study	Programmable
		Missing any scheduled or unscheduled C-SSRS	Programmable
		Missing all triplet measurements of blood pressure or pulse at any scheduled visit	Programmable
		Missing entire chemistry or hematology panel	Programmable
		No ECG measurements during a study phase	Programmable
Investigational Product	Patient took medication not fit for use		Nonprogrammable
	Unblinding		Nonprogrammable
	Other	IP lost or stolen	Nonprogrammable
		Dose planned but not given- date of injection missing	Programmable
		Dosing interval outside specified limits of 21-37 days for double-blind treatment phase	Programmable
	Dosing Error		Nonprogrammable
Safety	SAEs		Nonprogrammable
	Other	Positive pregnancy test	Nonprogrammable

Category	Subcategory	Study specific	Source
Data Quality	Treatment Assignment/Randomization Error	IWRS data entry errors that impact patient stratification	Programmable
	Treatment Assignment/Randomization Error	Randomized after screening failure, no study drug dispensed	Programmable
	Other	Primary efficacy compliance rate $\leq 50\%$ in any biweekly interval during DB treatment phase	Programmable
	Data Entry Issues	Patients did not report oxygen use in number of times in eDiary	nonprogrammable
Administrative Oversight	Patient Privacy Violation		Nonprogrammable
	Suspected Misconduct		Nonprogrammable
	Other	Post training, switching roles blinding to unblinded vice versa without prior medical team approval	Nonprogrammable
		Unqualified or untrained site personnel administer (C-SSRS)	Nonprogrammable
		Quality issue at site or vendor	Nonprogrammable

Abbreviations: ALP = alkaline phosphatase; ALT = alanine aminotransferase; CABG = coronary artery bypass grafting; C-SSRS = Columbia Suicide Severity Rating Scale; DB = double-blind; ECG = electrocardiogram; DVT = deep vein thrombosis; ePRO = electronic patient-reported outcome; I/E = inclusion/exclusion criteria; IP = investigational product; IWRS = interactive web-response system; MI = myocardial infarction; PCI = percutaneous coronary intervention; PE = pulmonary embolism; QTcB = Bazett's corrected QT interval; SP = study phase; TBIL = total bilirubin; UA = unstable angina; ULN = upper limit of normal.

